2.5.2. Comparator Group

NA as this is a single arm study.

Tramadol Infusion 07FEB2019

2.6. Treatment Assignment and Randomization

No randomization will be utilized in this study.

2.7. Sample Size Determination

A sample size of approximately 250 patients will be enrolled. This sample size of 250 patients will provide approximately 90% power to detect at least one incidence of uncommon adverse events (those events with a true underlying incidence of 1%).

3. GENERAL ANALYSIS AND REPORTING CONVENTIONS

This section discusses general policies to be employed in the analysis and reporting of the data from the study. Departures from these general policies are provided in the specific detailed sections of this SAP. When this situation occurs, the rules set forth in the specific section take precedence over the general policies.

All continuous study assessments will be summarized by time point (as applicable) using the descriptive statistics n, mean, SD, median, and range (minimum, and maximum). All of the categorical study assessments will be summarized by time point (as applicable) using frequency counts and rates of occurrence (%).

The treatment group will be labeled as '**Tramadol 50 mg**' for all outputs. All study data will be listed by study center, patient, and time point (as applicable).

No preliminary rounding will be performed; rounding will only occur after the analysis. To round, consider the digit to the right of the last significant digit: if <5, then round down; if \geq 5, then round up. Means and medians will be presented with one more decimal place than the precision of the raw data. Standard deviations will be presented with two more decimal places than the precision of the raw data. Percentages will be presented with one decimal place. Minimums and maximums will be presented with the same precision as the original data.

All analyses will be performed using the SAS System® version 9.3 or higher. The domain (Study data tabulation Model [SDTM]) and analysis (Analysis Data Model [ADaM]) data sets will be taken as input to the SAS programs that generate the report-ready tables, figures and listings. The submission ready SDTM and ADaM data sets will be provided to the sponsor along with display deliveries.

The following conventions will be used throughout the study analysis:

- Time T0 is the time of start of the first study drug administration.
- Study Day is defined as (Date of Assessment minus Date of First Dose of Study Medication). The first day of dosing is Study Day 0. The day immediately prior to first dose is Study Day -1. Study Day will be calculated for every record in the database and presented alongside the date fields in the data listings, where applicable. For instance, the start *date* of each TEAE will also have the Start *Day* presented in the listings.
- Assessment and visit times are defined relative to time T0.
- Baseline value is defined as the last valid measurement prior to the first treatment administration.
- Change from baseline is defined as post-baseline value minus baseline value.
- Unscheduled visits and measurements will be included in subject listings but will not be used in analyses.

- If duplicate values are obtained at a given visit (e.g., lab assay is repeated on a sample resulting in two results, or vital sign repeated during a visit), the last reported value will be used unless it is noted that the measurement was in error for that value.
- Values that compromise interpretation will not be used in summaries (e.g., values that were obtained post-dose will not be summarized as pre-dose values).

4. **PATIENT SUMMARIES**

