9.4. Clinical Laboratory Evaluation

Clinical laboratory test results (blood chemistry, hematology and urinalysis) will be listed for individual patients. Baseline for clinical laboratory parameters will be defined as the last evaluation before dosing with study treatment. For each individual lab test value, results and change from baseline will be summarized by time point (baseline and at discharge).

The number and percent of patients with potentially clinically significant (PCS) values will be summarized. Only new-onset PCS values, i.e., patients with pre-existing PCS values at pre-treatment will not be considered to have new-onset values on-treatment. The criteria used to identify potentially clinically significant laboratory values are listed in Table 3.

Variable Name (Normal Range)	Low	High
Hematology		
White Blood Cells (NR: 3.7 - 11.0x K/cu /mm)	$\leq 2.8 \text{ x } 10^3 \text{ /mm}^3$	$\geq 16 \text{ x } 10^3 \text{ /mm}^3$
Neutrophils (NR: 46 - 72%)	$\leq 15\%$	NA
Lymphocytes (NR: 14 - 46%)	NA	≥75%
Monocytes (NR: 0 - 11%)	NA	≥15%
Eosinophils (NR: 0 - 7%)	NA	≥10%
Basophils (NR: 0 - 3%)	NA	≥10%
Red Blood Cells Female: (NR: 3.8 - 5.1 x 10 ⁶ /mm ³) Male: (NR: 4.1 - 5.6 x 10 ⁶ /mm ³)	≤3 x 10 ⁶ /mm ³ ≤3.5 x 10 ⁶ /mm ³	$\geq 6 \ge 10^6 / \text{mm}^3$ $\geq 6.5 \ge 10^6 / \text{mm}^3$
Hematocrit		
Female: (NR: 36.4 – 48.9%)	≤32%	NA
Male: (NR: 41.6 – 54.1%)	≤37%	NA
Hemoglobin Female: (NR: 11.5 – 16.0 g/dL) Male: (NR: 13.0 – 17.5 g/dL)	≤9.5 g/dL ≤11.5 g/dL	NA NA
Platelets (NR: 125 - 375 K/cu /mm)	$\leq 75 \text{ x } 10^3 \text{ /mm}^3$	\geq 700 x 10 ³ /mm ³
Serum Chemistry		
Total protein (NR: 6.0 - 8.0 g/dL)	≤4.0 g/dL	≥10 g/dL
Albumin (NR: 3.5 - 5.5 g/dL)	≤2.0 g/dL	NA
Creatinine (NR: 0.7 - 1.4 mg/dL)	NA	$\geq 2 \text{ mg/dL}$
BUN (NR: 5 - 20 mg/dL)	NA	\geq 30 mg/dL
Uric Acid: (NR: 2.0 - 6.0 mg/dL	NA	≥9.0 mg/dL
Bilirubin total (NR: 0.1 – 1.1 mg/dL)	NA	$\geq 2.5 \text{ mg/dL}$
Bilirubin direct (NR: 0 - 0.4 mg/dL)	NA	≥0.6 mg/dL
Alkaline phosphatase (NR: 30 - 115 U/L)	NA	≥390 IU/L
AST/SGOT	NA	□150 U/L
ALT/SGPT	NA	□165 U/L
CPK (NR: 24 - 169 U/L)	NA	≥702 IU/L
Glucose random (NR: 60 - 115 mg/dL)	≤40 mg/dL	\geq 250 mg/dL
Calcium (NR: 8.5 - 10.5 mg/dL)	≤8.0 mg/dL	≥12 mg/dL

Table 3:List of Potentially Clinically Significant Ranges for Clinical Laboratory
Parameters (Study AVE-901-104)

Variable Name (Normal Range)	Low	High
Phosphorous (NR: 2.5 - 4.5 mg/dL)	\leq 1.7 mg/dL	NA
Sodium (NR: 133 - 145 mEq/L)	$\leq 126 \text{ mEq/L}$	$\geq 156 \text{ mEq/L}$

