9.5. Vital Signs

Vital signs results including BP (systolic and diastolic), heart rate, respiration rate, pulse oximetry, and temperature will be listed for individual patients. Baseline for vital signs measurements will be defined as the last evaluation before dosing with study medication. Vital signs and changes from baseline will be summarized by time point.

Vital sign parameter outcomes will be assessed for potential clinical significance; observed values and changes from pre-treatment to on-treatment time points will be tabulated for continuous parameters, as warranted.

The number and percent of patients with potentially clinically significant (PCS) values during the treatment phase will be summarized. A focus will be on new-onset PCS values, i.e., patients with pre-existing PCS values at pre-treatment will not be considered to have new-onset values on-treatment. The criteria for identifying potentially clinically significant vital signs values are provided in Table 4.

Table 4:List of Potentially Clinically Significant Ranges for Vital Sign Parameters
(Study AVE-901-104)

Variable Name	LOW	HIGH

Systolic BP	<86 mm Hg OR a decrease of ≥25 mm Hg from baseline	>200 mm Hg OR an increase of ≥25 mm Hg from baseline
Diastolic BP	<48 mm Hg OR a decrease of ≥20 mm Hg from baseline	>110 mm Hg OR an increase of ≥20 mm Hg from baseline
Heart rate ¹	1) <45 bpm OR a decrease of ≥25 bpm from baseline	1) >105 bpm and increase ≥25 bpm from baseline OR >125 bpm

¹ bpm: beats per minute

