9.7. ECG Examinations

ECG examination interpretation results and heart rate and interval duration results will be listed for individual patients. Baseline for ECG continuous measurements will be defined as the last evaluation before dosing with study medication. Continuous ECG values and changes from baseline will be summarized by time point. The proportion of subjects with Normal, Abnormal: Not Clinically Significant, and Abnormal: Clinically Significant will be summarized by time point.

The ECG analysis will include a careful review of QTcF values. As part of this review, a summary of the number (percent) of patients with QTcF values in the following ranges will be provided: \leq 450 msec, >450 to \leq 480 msec, >480 to \leq 500 msec, and >500 msec. This will be performed by visit as well as at ANY time during the treatment period (where the highest QTcF value will be used for that assessment).

The incidence of PCS values will be presented, with a focus on new-onset PCS values. The criteria for identifying potentially clinically significant ECG values are provided in Table 5.

Table 5:List of Potentially Clinically Significant Ranges for ECG Parameters (Study
AVE-901-104)

PR Interval	
High: >200 msec OR Increase ≥ 20 msec from baseline	
QRS Interval	
High: >100 msec OR Increase ≥ 10 msec from baseline	
QT Interval	
High: >500 msec OR Increase ≥ 60 msec from baseline	
QTcF Interval	

High: > 450 msec (Males); >470 msec (Females) OR Increase \geq 50 msec from baseline	;
--	---

Heart Rate

Low: <45 bpm OR a decrease of \geq 25 bpm from baseline

High: >105 bpm and increase \geq 25 bpm from baseline OR >125 bpm

Tramadol Infusion 07FEB2019

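### Unscheduled post-dose readings are listed but left out of the potentially clinically significant (PCS) counts, because SAP 9.4, 9.5 and 9.7 state no departure from the general rule in SAP 3

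*SAP*

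**What the plan says.** **General rule.** SAP 3 states: "Unscheduled visits and measurements will be included in subject listings but will not be used in analyses". It also says that a detailed section may provide a departure, and that in such a case "the rules set forth in the specific section take precedence over the general policies". SAP 7.2 points the same way, since it bases summaries on the nominal visits set by the protocol.

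**PCS paragraphs.**
- Laboratory (SAP 9.4): "The number and percent of patients with potentially clinically significant (PCS) values will be summarized". Only new-onset values count: "patients with pre-existing PCS values at pre-treatment will not be considered to have new-onset values on-treatment".
- Vital signs (SAP 9.5): "The number and percent of patients with potentially clinically significant (PCS) values during the treatment phase will be summarized". SAP Table 4 gives criteria for systolic pressure, diastolic pressure and heart rate only.
- ECG (SAP 9.7): "The incidence of PCS values will be presented, with a focus on new-onset PCS values". A separate paragraph summarises QTcF ranges by visit and at any time in the treatment period, using the highest value.

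**Planned output.** SAP 14.1.1 lists five PCS tables: chemistry, hematology, urinalysis, vital signs and 12-lead ECG.

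**Baseline.** SAP 3 has the general definition: "Baseline value is defined as the last valid measurement prior to the first treatment administration". SAP 9.4, 9.5 and 9.7 each define it again as the last evaluation before dosing.

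**The concern.** A PCS count asks whether a patient ever crossed a threshold after dosing. Leaving out off-schedule readings is sensible for means by time point, where an extra reading has no nominal slot. It suits an ever-crossed count poorly, because a valid value beyond the threshold is on file and still does not enter the numerator.

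Laboratory, vital-sign and ECG changes are named safety endpoints under the primary objective (SAP 2.1.1), so the PCS tables are among the main threshold-based outputs of the study. It is a reasonable inference, though the documents do not say so, that extra readings are often taken because something already looked abnormal. If so, the excluded readings are the ones more likely to cross a threshold.

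**Working it through.** **1. The plan's own figure.** The only probability in the plan is the sample-size statement in SAP 2.7: 250 patients, true incidence 1%, approximately 90%. Check: 1 − 0.99^250 = 0.919, which agrees. It concerns adverse events, and this point does not change it.

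**2. Is there a departure?**

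| Section | What the PCS text specifies | Are unscheduled readings mentioned? |
|---|---|---|
| SAP 9.4 | Number and percent of patients, new onset only | No |
| SAP 9.5 | Number and percent of patients over the treatment phase | No; a period is set, not a type of reading |
| SAP 9.7, PCS | Incidence, with a focus on new onset | No |
| SAP 9.7, QTcF ranges | By visit and any time, highest value | No; the any-time wording may be meant as a departure |

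With no departure stated, the SAP 3 rule applies to the PCS counts.

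**3. Direction.** Let S be a patient's scheduled post-dose values and U the unscheduled ones. The patient counts as PCS if any value used meets the threshold. Anyone counted from S is also counted from S and U together, so the count from S alone is less than or equal to the count from both. New-onset status depends on pre-dose values, which are the same in both counts. Dropping U can therefore only leave the count unchanged or lower it.

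**4. Room for off-schedule values** (Protocol 6.6.4 and 6.6.5). These figures describe the schedule, not the size of the effect.
- Laboratory: one scheduled post-dose sample, at End of Treatment, in a treatment period of up to 168 hours.
- ECG: scheduled after each infusion for the first 24 hours, then at End of Treatment. In the anticipated 48-hour course, doses fall at Hours 0, 2, 4, 8, …, 44, which is 13 doses. Those after Hour 24 are at 28, 32, 36, 40 and 44, which is 5, or 6 if the Hour 24 dose is included. So 5 to 6 of 13 infusions (38% to 46%) have no scheduled post-infusion ECG. In a 24-hour course (0, 2, 4, 8, 12, 16, 20) it is 0 of 7.
- Vital signs: 0.5, 1, 2, 3 and 4 hours (5 readings) plus 8, 12, …, 48 (11 readings) = 16 scheduled post-dose readings through Hour 48, then every 8 hours.

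**5. Size per patient.** With 250 treated, 1/250 = 0.4 percentage points in the table row concerned. The number of affected patients is not in the documents. For assumed counts of 1, 3 and 5:
- 1/250 = 0.4 points
- 3/250 = 1.2 points
- 5/250 = 2.0 points

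**The case against.** The strongest reply is that the exclusion is a deliberate, pre-specified choice, consistent with SAP 7.2, which keeps incidence independent of how often a site re-measures. The study is descriptive. The values stay in the listings, a central reader reviews ECGs patient by patient (SAP 9.1), and clinically significant findings may be recorded as adverse events (Protocol 11.2.1.1). All of this stands and holds the severity down. None of it gives the proportion of patients who crossed a stated threshold, which is what the PCS tables are for.

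The vital-sign wording in SAP 9.5 covers the whole treatment phase, and a programmer could take it to admit every reading in that period. That reading is possible, so this case is less certain than the laboratory one. Table 4 also has no criteria for SpO2, respiratory rate or temperature, so no reading of those could enter the PCS count, whether scheduled or not.

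A reader might go further in three ways that the documents do not support:
- *That baseline is also undefined for unscheduled readings, so the error could run in either direction.* SAP 9.4, 9.5 and 9.7 each take the last evaluation before dosing, without limiting it to scheduled readings. Under SAP 3 those sections take precedence. For laboratory tests, SAP 2.3.1 names the central laboratory as the source.
- *That the any-time QTcF summary is wrong.* It is ambiguous: its wording may already be a departure, but it does not say whether unscheduled ECGs enter.
- *That repeats within a scheduled visit are lost in the same way.* Those fall under the separate SAP 3 rule for duplicates (last reported value unless noted as an error), which this point does not dispute.

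**Conclusion.** The point holds for the PCS counts. As written, the SAP leaves out a patient whose only post-dose PCS value is unscheduled. It is firm for the three laboratory tables, nearly as firm for the ECG PCS table, and less certain for blood pressure and heart rate.

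The effect is one-sided: the count stays the same or falls, by 0.4 percentage points per affected patient. That figure assumes 250 treated patients. The Safety Population may be smaller, because patients can be withdrawn after surgery and before dosing (Protocol 7.2.1) and withdrawals are not replaced (Protocol 6.2); each patient would then weigh slightly more. The totals of 1.2 and 2.0 points rest on assumed counts, so the documents do not support a claim that PCS incidence is materially understated.

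Nor would it be right to infer that the adverse event tables or the 1% detection statement are weakened. Neither uses the PCS rule. This is a cheap improvement of low-to-moderate severity.

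**What to change.** Add to SAP 9.4, 9.5 and 9.7:

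> As a departure from Section 3, PCS incidence (and, in 9.7, the any-time QTcF categories) includes unscheduled as well as scheduled values after the first dose through End of Treatment, except documented measurement errors.

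In addition:
- State in SAP 9.4 whether post-dose results from a local laboratory count.
- Leave the SAP 3 duplicate rule and the by-time-point summaries as they are.
- Footnote each of the five PCS tables with the number of patients identified only by an unscheduled value.

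The cost is a few sentences, a record-selection flag and five footnotes. The values are already due to appear in the listings, so no new data are needed. The change should be made before database lock, since SAP 1 requires analyses added after lock to be labelled post hoc.

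The downside is that incidence may be slightly higher and will depend partly on how often sites re-measure. The footnote makes this visible and lets the scheduled-only count be recovered by subtraction. That also helps if the other two Phase 3 studies due to be combined with this one (Protocol 4.4) follow a different rule, which these documents do not show.

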4.1. Analysis Populations

Three population are identified for purposes of the statistical analysis:

- Screened Population, defined as all screened patients.
- Screened Not Treated, defined as the subset of patients who are screened but not treated due to not moving forward to surgery or not meeting post-surgical dosing criteria.
- The Safety Population is defined as all patients who receive study medication. Patients will be analyzed according to the actual treatment they receive.

In general, data listings will include only subjects who receive study treatment (Safety population).

4.2. Disposition of Patients

Disposition of all patients screened will be tabulated. The Inclusion/Exclusion criteria failed for screen failures will be presented. The denominator will be based on all screened patients.

Patient completion status (completer, screen failure, or post-op failure) and reasons for study completion will be tabulated descriptively in a patient disposition summary table. Reasons for study completion include:

- Dosing Completed (patient discharged and did not stop dosing for the other items listed below)
- Adverse Event
- Lost to Follow-Up
- Death
- Protocol Violation
- Subject Non-compliance or uncooperativeness
- Withdrawal of Consent
- Other

The number of days in the study will also be summarized. The number of days is computed as: [Date of study completion (i.e., date of discharge) or withdrawal minus the date of first treatment administration (Day 1)] + 1.

All patient disposition data will be presented in listings.

4.3. **Protocol Deviations**

Protocol deviations will be documented in the electronic case report from (eCRF), categorized according to type of deviation (e.g., out of window, etc.) and classified as major or minor by the Sponsor's medical monitor. Protocol deviations, both minor and major, will be presented in a

data listing and major violations will be summarized by category of deviation and classification. A listing describing patients excluded from the Per Protocol Population will be provided.

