
Statistical methods:
 
Sample Size
 
A sample size of approximately 250 patients will be enrolled. This sample size of 250 patients will provide approximately 90% power to detect at least one incidence of uncommon adverse events (those events with a true underlying incidence of 1%).
 
General Statistical Methods
 
This is an open-label study in which the objective is to assess the safety of Tramadol for post-surgical pain in patients having elective surgery. The statistical methods utilized will be consistent with this objective.
 
Outcomes will be tabulated utilizing descriptive methods only (e.g., mean, standard deviation, median, min, max for continuous variables, and number and percent for categorical variables).
 
The baseline for all variables will be the last measurement obtained prior to the patient receiving the first dose of study drug.
 
Patient disposition (including the number and percent of patients who are enrolled, who receive treatment, who prematurely discontinue and reasons for discontinuation, and who complete the study) will be tabulated. The number (%) of patients by exposure (number of doses given, total dose given, time from first dose to last dose) will be tabulated.
 
Study Populations
 
The Safety Population is defined as all patients who receive at least one dose of study medication. This will be the primary population for which conclusions will be drawn.
 
Alpha Levels
 
No inferential testing is planned for this safety-based study. If inferential statistics are used, they will only be applied to allow for better understanding of any treatment effects, but will not be used for hypothesis testing.

Protocol AVE-901-104 Phase 3 Open-Label Safety Study
Avenue Therapeutics, Inc.

Tramadol Infusion
August 29, 2018

Name of Sponsor/Company: Avenue Therapeutics, Inc.
Name of Investigational Product: AVE-901 (Tramadol)
Name of Active Ingredient: Tramadol for intravenous infusion

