7.2.1. Post-Surgical Additional Exclusion Criteria

The patient is to be evaluated post-operatively prior to the initial treatment with the study drug and will be withdrawn prior to treatment with the study drug if any of the following exclusion criteria are met:

1. Patients who, in the opinion of the investigator, are not likely to tolerate the protocol's allowed analgesic regimen (tramadol plus non-opioid adjuvants).
2. Patients who have been admitted to the ICU post-surgery or have experienced complications during the surgical procedure that would put them at increased risk from receipt of the investigational product in the opinion of the investigator.
3. The patient is not clinically stable and not able to answer questions and follow commands.
4. The patient has evidence of respiratory insufficiency, such as a respiratory rate that is less than 8 breaths per minute or arterial oxygen saturation by pulse oximetry of less than 90% with supplemental oxygen.
5. Use of 5-HT₃ antagonists (e.g. ondansetron, granisetron, palonosetron) preoperatively, intraoperatively, or postoperatively

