12.6. Patient Disposition

Patient completion status and reasons for end of treatment will be tabulated descriptively.

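### Does the SAP's disposition section count treated patients who stop early as completers?

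*SAP*

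**What the plan says.** SAP section 4.2 sets out the disposition display: "Patient completion status (completer, screen failure, or post-op failure) and reasons for study completion will be tabulated descriptively". Just before that it covers the criteria failed by screen failures and adds: "The denominator will be based on all screened patients". The table list in SAP 14.1.1 puts Table 14.1.1 on all screened subjects.

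Section 4.2 then lists eight reasons. The first is "Dosing Completed (patient discharged and did not stop dosing for the other items listed below"). The other seven are adverse event, loss to follow-up, death, protocol violation, non-compliance, withdrawal of consent, and other. The days-in-study formula in the same section starts from "Date of study completion (i.e., date of discharge) or withdrawal minus the date of first treatment administration".

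SAP 4.1 describes its untreated group as "screened but not treated due to not moving forward to surgery or not meeting post-surgical dosing criteria". This matches Protocol 7.2.1, under which a patient "will be withdrawn prior to treatment with the study drug if any of the following exclusion criteria are met".

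The protocol speaks to disposition twice. The synopsis wants the number and percent of patients enrolled, treated, "who prematurely discontinue and reasons for discontinuation, and who complete the study". Section 12.6 is shorter: "Patient completion status and reasons for end of treatment will be tabulated descriptively".

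**The concern.** Two of the three listed statuses belong to patients who never received study drug. By elimination, a treated patient who stopped for an adverse event or withdrew consent has only the label completer. The SAP's vocabulary encourages that reading: it calls all eight reasons, death included, reasons for study completion. The title of Table 14.3.1.3.1 also says completion where its sibling tables say discontinuation.

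The synopsis treats premature discontinuation and completion as separate categories, and SAP section 12 declares no departure from the protocol. On the literal reading, the disposition table could show every treated patient as a completer. Early stops would then have to be added up from the reasons, on a base that includes people who were never dosed. In a single-arm safety study with open-ended treatment, the share of treated patients who stopped early is basic context for exposure, so the question deserves a check.

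**Working it through.** No figure in the plan is at issue, so the main check is of the text. A short illustration of the denominator follows.

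**1. Is completer defined to include early stoppers?** No. The word appears once, in a bracketed list, without a definition. The elimination argument needs that list to be exhaustive, and the same section shows that it is not meant to be:
- The first reason is defined by contrast: the patient was discharged and did not stop dosing for any other listed item. That already divides treated patients into those who finished dosing and those who stopped.
- The days-in-study formula allows for completion or withdrawal as two different endings.
- Listing 16.2.5, on the Safety Population, covers completion and early termination.

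The reading that fits all three is that completers are the patients whose dosing was completed. It also suits the design. Treatment is expected to last from Hour 0 to Hour 48 and may run to Hour 168, so no fixed number of doses marks completion and only the reason can.

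**2. Can the synopsis request be met from what is planned?** Largely, from these items:
- Early stops: treated patients minus those with dosing completed, from the reasons in Table 14.1.1.
- Treated N: Table 14.1.2 and the exposure table (14.1.7), both on the Safety Population.
- Reasons: tabulated in Table 14.1.1 and listed by patient. Protocol 7.3 requires a primary reason on the End of Study eCRF, so the data exist.
- Adverse-event discontinuations: Table 14.3.1.3 and its subgroup versions on the Safety Population, plus a line in the overall TEAE summary (SAP 9.2).
- Extent of treatment: doses, total mg and duration in SAP section 6, with a cumulative exposure figure.

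**3. Does the screened base contradict the protocol?** No. The synopsis asks for number and percent but names no denominator, and neither does section 12.6. The SAP sentence directly follows the one on screen failures and may govern only that display.

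**4. What would the screened base do to a percentage?** The documents give no early-stop rate, no treated number and no screened number, so every input here is an assumption. Let T be treated, S screened and d the early-stop fraction among treated patients. The screened-based percentage is d × T/S.
- Take T = 250 (the planned enrolment) and 25 early stops: 25/250 = 10.0%.
- S = 300: 25/300 = 8.3%. S = 400: 25/400 = 6.25%.
- Enrolment precedes surgery, some patients may not be dosed, and withdrawals are not replaced, so T could be lower. For T from 200 to 250 and S from 300 to 400, T/S runs from 200/400 = 0.50 to 250/300 = 0.83.
- On the literal reading with S = 300, completers would be 250/300 = 83.3%. On the ordinary reading they are 225/300 = 75.0%.

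The count of 25 does not change, and multiplying by S/T restores the treated-patient rate: 8.33% × 300/250 = 10.0%. Both S and T are reported.

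**The case for a change.** The strongest case for a change is that the synopsis requires a count and percentage of premature discontinuations, and the SAP names no row for it. Adverse-event tables do not cover stops for other reasons, and a listing is not a tabulation. A programmer must decide what completer means, and one who took the three-status list literally would produce a misleading row. The repair would be a line of text using data already collected.

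Much of this is true as description. The status list is incomplete, the word is undefined, and a treated-patient column would be good practice. What does not stand is the step from an undefined word to a wrong result. The layout of Table 14.1.1 is not in the documents, only its title and population, so the claim that it would show all treated patients as completers is a prediction. The reasons in that same table would expose such a row at once.

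The obvious repair also needs care. Labelling every treated patient without completed dosing as an early stopper could capture someone who was fully dosed and then recorded as lost before the Day 14 call. SAP 4.2 takes discharge as the completion date, which makes this less likely, but how sites record it depends on an eCRF page that is not in the documents. Stopping treatment and leaving the study are different events, and the reasons shown separately keep them visible.

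**Conclusion.** No change to the plan is needed. SAP 4.2 leaves completer undefined and omits a status for treated patients who stop early. The surrounding text supplies the sensible meaning, and the planned outputs carry the information the synopsis asks for. Naming the row and adding treated-patient percentages is table-programming detail that the study team would settle in the ordinary course. The wording of the Table 14.3.1.3.1 title is a clerical slip.

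The possible effect is confined to one descriptive table: how one row is labelled, and percentages that would read at 0.50 to 0.83 of the treated-patient rate under the assumed 200 to 250 treated and 300 to 400 screened. Adverse event, laboratory, vital sign and ECG summaries use the Safety Population and are untouched. The conclusion rests on two assumptions: that stop reasons are recorded for treated patients, as Protocol 7.3 requires, and that they are tabulated, as SAP 4.2 states.
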